5.3 Effectiveness

Overall Best Response

Overall best response for a patient is the best-observed disease response based on all response assessments available for each patient up to reported PD and prior to any subsequent anticancer therapy. The assessments of SD must occur at least once on or after day 42 to be considered for best response.

Objective Response (OR)

Objective response is defined as a best tumor response assessment of either complete response or partial response. Patients who prematurely discontinue without a tumor assessment will be considered non-responders.

Disease Control (DC)

Disease control is defined as a best tumor response assessment of CR, PR, or SD. Patients without a post-baseline tumor disease assessment will be considered to not have disease control.

Thus, for all patients:

If overall best tumor response = CR, PR or SD then: DC=1

Otherwise: DC=0

Progression-free Survival (PFS)

Time (in months) from day 1 to the earliest date of disease progression as reported by the investigator or death, regardless of cause, (whichever is first). Patients with no reported disease progression and alive will be censored at last contact date/last date known alive.

PFS = (date of progressive disease or death - date of day 1) / 30.4375

All tumor assessment dates will be based on the actual imaging dates reported by the investigator.

Overall Survival

Overall survival time is calculated as the number of days from day 1 to death (date of death - date of first dose). Time to death will be summarized in months. Patients who have not died (no record of death) or are lost to follow up will be censored at the date of last contact/last date known alive.

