3 METHODS

3.1 Study Design Overview

This will be a non-interventional, prospective, multicenter study in which trabectedin + PLD will be administered according to standard local clinical practice following approved SmPC indication and dose. There will be no involvement with any treatment decisions for the patients included in the study. The choice of therapy must be made prior to the patient's inclusion in the study. Treatment administration will be independent of, and dissociated from participation in the study.

For each patient, the study will consist of a Qualification Period (see Section 6.1), an Observation Period (see Section 6.2) and a Follow-up Period (see Section 6.3). Once treatment with trabectedin is discontinued, patients may be treated with subsequent anticancer therapies or supportive care as per the treating clinician's best clinical judgment. The study design is summarized in Appendix 14.1, Figure 1.

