6.3 Follow-up Period

A follow-up visit will take place 1 month after the end of the Observation Period. For patients who discontinued trabectedin before 12 months after the Index date, an additional follow-up visit will be performed 12 months after the Index date, except for patients who are dead or have withdrawn consent. Follow-up information may be collected through phone calls with the patient or site visits by the patient.

For each follow-up visit, the following data will be collected, if available:

- Safety assessment (all AEs including ADRs and SADRs). Laboratory tests associated with ADRs and SADRs will be collected when available.
- Reason for discontinuation of treatment with chemotherapy, if applicable. Reason will include the following: treatment completed, PD, toxicity including grade, patient refusal, patient lost to follow-up, withdrawal of consent, inter-current illness of sufficient severity (specify), withdrawal for pregnancy, death (specify the cause), or other (specify).

- Best symptomatic response and best response (except for patients with confirmed PD at discontinuation or who had started a new treatment) and evaluation of treatment duration.
- Survival status.
- Subsequent non-trabectedin anti-cancer treatments that the patient received during the follow-up period, including regimen number, type of therapy, start and stop date, and best response observed for each regimen.

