7 STUDY ASSESSMENTS

Observations and measurements collected, if available, during each study cycle are described in Table 1 located below and in Appendix 14.1, Figure 1.

18 September 2018 Confidential Trabectedin + PLD

PharmaMar Page 27

Table 1. Study Schedule of Events

Assessment/Activity	Qualification Period		Observation Period		Follow-up
	Patient Qualification	ICF Signature Date	Baseline and Cycle 1 Visit	Subsequent Visits	Period
Review of inclusion/exclusion criteria	X ¹				
Signed Informed Consent Form (ICF)		X			
Medical history			X^2		
Prior therapies			X		
Initial imaging			X^3		
Physical examination (BSA, weight, and height)			X	X^4	
Performance status (ECOG/WHO score)			X	X^4	
Date of first trabectedin + PLD administration			X^5		
Prior trabectedin + PLD therapy			X		
Safety assessment (AEs including ADRs and SADRs)			X	X^4	X
Laboratory tests			X	X^4	X^6
Reporting of symptomatic and best response			X^8	X^4	X
Additional imaging ⁷			X	X^4	X^7
Reason for ending treatment with trabectedin + PLD			X	X	
Survival status			X	X	X

Abbreviations: ADRs, adverse drug reactions; AE, Adverse Event; BSA, body surface area; ECOG, Eastern Cooperative Oncology Group; SADRs, serious adverse drug reactions; WHO, World Health Organization.

18 September 2018 Confidential Trabectedin + PLD

¹Information must be collected prior to first on-study trabectedin administration (Cycle 2 or later) but may occur on the same day.

²This includes relevant prior history, the description of key features of the disease and disease histology.

³The patient's baseline tumor imaging assessment will be considered the imaging assessment performed prior to the initial trabectedin + PLD administration (1st treatment cycle) or the earliest imaging study following the 1st treatment cycle.

⁴Repeat at the treating clinician's typical schedule.

⁵If patient enrollment occurs after the second administration of trabectedin + PLD or later, information on physical examination (BSA) and performance status should also be collected for Cycle 1 trabectedin + PLD administration, when available.

⁶Safety assessments include laboratory tests associated with ADRs and SADRs and will be collected when available.

⁷The final imaging assessment will be the imaging assessment performed closest to the Follow-up Visit and prior to initiation of any other chemotherapy treatments.

⁸Collected from cycle 2 and onward.

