10.3 Study Endpoints

The primary endpoint is the PFS measured as time from first dose of trabectedin to disease progression as reported by the investigator or death regardless of cause.

The secondary endpoints include the following:

- 1. Response rate (CR + PR)
- 2. Disease control rate (CR + PR + SD)
- 3. OS
- 4. ECOG/WHO PS
- 5. Treatment duration (number of cycles)
- 6. Treatment exposure
- 7. Time to next treatment
- 8. Safety of the combination of trabectedin + PLD

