9.4.2 Analyses of Effectiveness Secondary Endpoints

Objective Response

Objective response is defined as a best tumor response of complete or partial response as reported by the investigator in the overall response evaluation. Patients without an assessment of disease response will be treated as non-responders.

Descriptive statistics will be provided for best overall tumor response. The number and percentage of patients within each category of best response (CR, PR, SD, PD, and not evaluable (NE) (including reported in the electronic case report form (CRF) as not evaluable) and not done (including not assessed, not reported, and not done) will be presented. The proportion will be estimated by dividing the number of patients within each category of response by the number of patients available in the full analysis set. Each patient will be counted within only one response group, with the best response during the study (from the start of the treatment until the end of study treatment or PD, whichever occurs first), as reported by the investigator. No confirmation of response requirement will be applied for this analysis. Objective response rate (CR + PR) and two-sided exact binomial 95% confidence intervals will be presented. Additionally, descriptive

statistics for objective response will be presented stratified on BRCA 1/2 status (positive, negative, unknown).

Disease Control

The disease control will be reported along with two-sided exact binomial 95% confidence intervals.

Overall Survival

OS will be descriptively analyzed as done for the primary endpoint PFS.

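### SAP 5.3 ends best response at the next anticancer therapy but gives PFS no rule for therapy started before progression, so PFS can include next-line time without planned tumour assessment

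*SAP*

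**What the plan says.** **PFS.** SAP 5.3 defines it as "Time (in months) from day 1 to the earliest date of disease progression as reported by the investigator or death, regardless of cause". Its censoring rule is "Patients with no reported disease progression and alive will be censored at last contact date/last date known alive". Protocol 10.3 uses the same events. Protocol 10.4.3 and SAP 9.4.1 add only the Kaplan-Meier method and its confidence intervals. None of these sections mentions subsequent therapy, and no sensitivity analysis of PFS is planned.

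**Response and exposure.** The same SAP section limits best response to "response assessments available for each patient up to reported PD and prior to any subsequent anticancer therapy". SAP 9.4.2 gives a narrower window, "from the start of the treatment until the end of study treatment or PD, whichever occurs first". SAP 5.2 caps treatment duration and the length of the last cycle at the start of the next anticancer treatment.

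**Stopping and switching.** Protocol 3.1 states: "Once treatment with trabectedin is discontinued, patients may be treated with subsequent anticancer therapies or supportive care". It does not require PD first. Protocol 6.3 lists completed treatment, toxicity and patient refusal as reasons for stopping, separately from PD.

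**Follow-up data.** Protocol 6.3 collects "Best symptomatic response and best response (except for patients with confirmed PD at discontinuation or who had started a new treatment"). It lists survival status and the start and stop dates and best response of each later regimen, but no PD date. Footnote 7 to Table 1 defines the final imaging as the one "closest to the Follow-up Visit and prior to initiation of any other chemotherapy treatments".

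**The concern.** The plan foresees a patient who stops without PD and starts something else. It sets a rule for that event for response and for exposure, but not for the primary endpoint.

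Following PFS through later therapy can be a deliberate choice, but it needs progression to be sought after the switch. Here the Observation Period ends with trabectedin (Protocol 6.2). What remains is one contact a month later and one at 12 months after the Index date, with response no longer requested once a new treatment has begun. If nobody reports a PD, the patient counts as progression-free up to last contact.

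Two things could then add to the reported PFS: any real effect of the next treatment, and time in which progression was not looked for. The primary objective is PFS after trabectedin + PLD, and a reader could not tell how much of the estimate comes from either source.

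**Working it through.** There is no figure in the plan to reproduce. The sample size of at least 300 rests on a judgement of sufficient accuracy, with no median or interval width.

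**Rules side by side**

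| Quantity | Rule when new therapy starts before PD |
|---|---|
| Best response (SAP 5.3) | stops |
| Best response (SAP 9.4.2) | already stopped at end of study treatment |
| Treatment and last-cycle duration (SAP 5.2) | capped |
| PFS (SAP 5.3, 9.4.1; Protocol 10.3) | none; runs to reported PD, death or last contact |
| Response at follow-up (Protocol 6.3) | not collected |
| Start date of new therapy (Protocol 6.3) | collected |

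**Size, under assumptions**

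- From the documents: median PFS 9.7 months (platinum-sensitive patients on the combination in OVA-301, Protocol 1.1.3.1).
- Assumed: exponential PFS; a share f of patients PD-free at ts = 4.5 or 6 months switches; the progression hazard is then multiplied by 0.7 or 0.5; every PD is reported.

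With h = ln 2 / 9.7 = 0.0715 per month and h2 = 0.7h or 0.5h, the curve after ts is

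S(t) = exp(-h·ts) × [(1 - f)·exp(-h(t - ts)) + f·exp(-h2(t - ts))].

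Solving S(t) = 0.5 gives:

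| f | ts | hazard ratio 0.7 | hazard ratio 0.5 |
|---|---|---|---|
| 10% | 4.5 | 9.87 | 10.00 |
| 10% | 6 | 9.82 | 9.91 |
| 20% | 4.5 | 10.05 | 10.33 |
| 20% | 6 | 9.94 | 10.14 |

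The rise runs from 9.82 - 9.7 = 0.12 to 10.33 - 9.7 = 0.63 months. The PD-free share is 0.725 at 4.5 months and 0.651 at 6, so f = 10-20% means about 6.5-14.5% of all patients.

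A simulation with switches spread over months 4 to 7 and follow-up capped at 13 months agrees. With about 7% and 14% of all patients switching, the SAP rule gives medians of 9.84-9.97 and 9.94-10.22. Censoring at the switch gives about 9.7. PFS at 12 months is 0.7 to 2.2 percentage points higher under the SAP rule.

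**If PD after the switch goes unrecorded.** Suppose only death ends PFS, with a hazard from the 27.0-month median OS in Protocol 1.1.3.1. The same formula then gives 9.98-10.10 (f = 10%) and 10.30-10.57 (f = 20%). This is a missing-data effect and is not part of the 0.1-0.6 range.

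**Against sampling error.** Expected events by 13 months: 300 × (1 - exp(-0.0715 × 13)) = about 182. The 95% interval for the median is 9.7 × exp(±1.96/√182), about 8.4 to 11.2.

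**Higher-risk switchers.** Take ts = 5 and f = 20%. Let switchers' hazard be 2h without the new therapy and 0.7 × 2h = 1.4h with it. The median without any switch is 8.99, the SAP rule gives 9.37, and censoring at the switch gives 9.7.

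**The case against.** *PFS regardless of later therapy is a recognised strategy, and the protocol and SAP agree on it.* This stands. A reader might infer that the primary definition is wrong, or that it contradicts the response rule. The documents do not support that: the two endpoints answer different questions. What is missing is a stated strategy and a second analysis.

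*The plan does not forbid PD dates after a switch.* This stands too. The Protocol 6.3 exemption names best response, not progression. Best response to later regimens is collected, Protocol 4.4.1 encourages continued follow-up, and footnote 7 concerns chemotherapy only. So a reader should not conclude that progression after a switch is excluded; its collection is simply not planned explicitly.

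*Next-line use is already described.* In part. Time to next treatment is a secondary endpoint, and SAP 9.4.4 summarises the next therapy, which SAP 9.1 presents by prior antiangiogenic use. Neither says how many patients switched before PD.

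*Censoring at a switch may be informative.* It may, as the higher-risk example shows: there the SAP rule still lies above the no-switch median, but censoring lies further above it. The second analysis should stand beside the first, not replace it.

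*Surgery is a separate matter.* Agreed. The SAP 5.3 response rule does not name surgery. The resection discussed in Protocol 1.1.1 concerns relapse after a treatment-free interval of over 24 months, and SAP 9.5.5 only summarises whatever surgery is reported.

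**Conclusion.** The gap is real and limited. The primary PFS can include next-line time in which tumour assessment is not planned, and nothing in the plan would show how much. The likely effect is a longer PFS: about 0.1-0.6 months on the median if 10-20% of PD-free patients switch at 4.5-6 months, the hazard ratio afterwards is 0.5-0.7, and switchers otherwise resemble the rest. The share, timing and effect are all assumed. The shift lies inside the sampling interval, but it is systematic, so a larger sample would not remove it. Which of the two analyses gives the longer PFS depends on who switches.

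A reader might go further and infer that the comparison by prior antiangiogenic use is biased, because untreated patients still have an antiangiogenic open to them. The documents do not show this. They do not describe next-line use by group or bar re-use in pretreated patients, and the group results are descriptive. It is a reason to report counts by group, not a finding.

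**What to change.** - **Primary analysis:** leave it unchanged, and say in SAP 5.3 that it follows patients through later therapy. Where a site already holds a PD date after a switch, use it.
- **Sensitivity analysis (SAP 5.3 and 9.4.1):** pre-specify one further PFS analysis, overall and by prior antiangiogenic use. Patients who start subsequent anticancer drug therapy before PD are censored at their last tumour assessment before that therapy.
- **Counts:** report the number of such patients overall and in each group.
- **Surgery:** subsequent ovarian cancer surgery can be treated the same way by its date alone. SAP 9.5.5 plans a time-to-surgery summary, which implies that dates exist, but procedure type is uncoded free text.
- **Interpretation:** state that censoring at new therapy may be informative, so the two analyses are read together.

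The cost is one SAP paragraph, one table and one Kaplan-Meier figure. Drug start dates are already collected. Adding a PD-date item to Protocol 6.3 is optional: it would need an amendment under Protocol 11.5, signed by treating clinicians and approved by ethics committees, for about 70 sites in five countries.

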4.3 Selection Criteria

If patients meet the selection criteria, they will be invited to participate in the study. Before any study-specific data are recorded, patients will be provided with all the study details prior to their decision to participate and will be requested to sign an informed consent form (ICF) prior to their participation in the study.

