6 STUDY PROCEDURES

This is a non-interventional study. Prior to the initiation of the qualification process or any study procedures, patients must sign an ICF indicating that they understand the purpose and procedures required for the study and that they are willing to participate in the study. The ICF must be signed 1 or more days following completion of the initial trabectedin + PLD administration (1st treatment cycle). The Study Schedule of Events is noted in Table 1 and Appendix 14.1, Figure 1.

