6.1 Qualification Period

The patient's inclusion/exclusion criteria will be evaluated before the patient signs the ICF. The Qualification Period will begin following the signing of the ICF and end with the first on-study trabectedin + PLD administration cycle.

The first on-study trabectedin + PLD administration must follow, but may be on the same day as the signing of the ICF and the evaluation of the patient's inclusion/exclusion criteria

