5. DEFINITIONS

5.1 General

Study Day 1

Will be defined as-the first day with trabectedin + PLD administration therapy.

Baseline Tumor Imaging

The patient's baseline tumor imaging will be considered the imaging performed prior to the initial trabectedin + PLD administration (Day 1) or the earliest imaging study following Day 1.

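### OS and PFS run from the first dose but patients enrol only after it, and Kaplan-Meier without an entry time biases both upward by an amount the documents do not let one fix

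*SAP*

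**What the plan says.** SAP 5.1 sets Study Day 1 as "the first day with trabectedin + PLD administration therapy". SAP 5.3 measures PFS as "Time (in months) from day 1 to the earliest date of disease progression as reported by the investigator or death, regardless of cause" and gives OS the same origin: "Overall survival time is calculated as the number of days from day 1 to death (date of death - date of first dose". Protocol 10.3 agrees: "The primary endpoint is the PFS measured as time from first dose of trabectedin to disease progression".

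Enrolment comes later. Protocol 4.3.1 requires at least one cycle before inclusion, and Protocol 6 states "The ICF must be signed 1 or more days following completion of the initial trabectedin + PLD administration (1st treatment cycle". Under Protocol 6.1, "The first on-study trabectedin + PLD administration must follow, but may be on the same day as the signing of the ICF"; footnote 1 of Table 1 puts that dose at cycle 2 or later. No upper limit on earlier cycles is given. Protocol 6.2.1 foresees enrolment after the second administration or later, with earlier data collected retrospectively.

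The full analysis set (SAP 6.1) contains enrolled patients only. SAP 9.1, 9.4.1 and 9.4.2 specify Kaplan-Meier for both endpoints, including fixed-time estimates, with no entry time. Three provisions come near the issue: SAP 9.2 tabulates time from first dose to consent, SAP 8.3 logs non-participation, and SAP 8.4 says assumptions will be assessed and alternative methods may be used. The planned tables and figures (SAP 11) include no delayed-entry output.

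**The concern.** Time between first dose and consent is free of deaths by construction, because a patient must be alive to consent. Counting that time as time at risk is left truncation handled as if it were full observation, and it raises the OS curve. PFS inherits the effect, since a patient lost to death before consent is also a lost PFS event.

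Follow-up ends about 12 to 13 months after the Index Date (Protocol 3.2, 6.3), while the platinum-sensitive patients cited in Protocol 1.1.3.1 had a median OS of 27.0 months. Median OS will probably not be reached, so readers will rely on fixed-time OS, which is the affected quantity. If the consent delay differs by prior antiangiogenic use, the two descriptive curves are also biased unequally.

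**Working it through.** **No plan figure to reproduce.** The sample size of at least 300 comes with no precision target, so nothing in the plan can be checked against this bias.

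**Inputs from the documents.** Median OS 27.0 months and median PFS 9.7 months (Protocol 1.1.3.1, platinum-sensitive patients on the combination, used for illustration); 3-week cycles; n = 300; month = 30.4375 days (SAP 5.3).

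**Assumptions.** Consent time E is uniform from day 2 to day 21, 42, 63 or 126 (end of cycle 1, 2, 3 or 6). Survival is Weibull, S(t) = exp[−ln 2 · (t/m)^k], with k = 1.0 (exponential) or k = 1.5 (lower early mortality).

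**OS.** Beyond the last entry time, plain Kaplan-Meier estimates S(t) / P(T > E), where P(T > E) is S averaged over E.

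| Consent by end of cycle | P(T > E), k = 1.0 | 12-month OS, true 73.5% | P(T > E), k = 1.5 | 12-month OS, true 81.4% |
|---|---|---|---|---|
| 1 | 0.990 | 74.2% | 0.999 | 81.5% |
| 2 | 0.982 | 74.9% | 0.997 | 81.7% |
| 3 | 0.973 | 75.5% | 0.994 | 81.9% |
| 6 | 0.948 | 77.5% | 0.983 | 82.8% |

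For example, 73.5 / 0.948 = 77.5.

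**Against sampling error.** The 95% CI half-width at n = 300 is about 4.9 points (1.96 × √(0.735 × 0.265 / 300) = 0.050). In 4,000 simulated studies censored 12 months after consent, the planned interval for 12-month OS covered the truth in 94.3, 92.2, 88.2 and 66.2% of samples (k = 1.0) and in 94.9, 95.0, 95.2 and 91.1% (k = 1.5). In a separate exponential simulation of 600 studies per delay pattern, with assumed mean delays of 13, 36 and 62 days, plain Kaplan-Meier never reached median OS.

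**PFS, losing only deaths before consent.** The median read off the curve solves S_PFS(t) = 0.5 · P(T_OS > E), so t = 9.7 · [−ln(0.5 · P) / ln 2]^(1/k).
- k = 1.0: 9.84, 9.96, 10.08 and 10.45 months. For six cycles, −ln(0.474) / 0.693 = 1.077, and 1.077 × 9.7 = 10.45.
- k = 1.5: 9.71 to 9.86 months.

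**Does delayed entry help?** Root mean square error of 12-month OS in points, n = 300:

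| Consent by end of cycle | Plain, k = 1.0 | Delayed entry from first patient, k = 1.0 | Delayed entry from 30 at risk, k = 1.0 | Plain, k = 1.5 | Delayed entry from 30 at risk, k = 1.5 |
|---|---|---|---|---|---|
| 1 | 2.64 | 2.77 | 2.63 | 2.25 | 2.27 |
| 2 | 2.86 | 3.04 | 2.71 | 2.23 | 2.26 |
| 3 | 3.25 | 3.49 | 2.84 | 2.24 | 2.29 |
| 6 | 4.67 | 4.15 | 3.05 | 2.58 | 2.45 |

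Starting at a minimum risk set matters because the earliest risk sets are tiny.

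**Where it fails.** Delayed entry estimates S(t) / S(earliest entry). If everyone enters at day 21, S(21 days) = 0.982 and both curves read 73.5 / 0.982 = 74.8%. Simulated consent on days 21 to 24 gave about 74.7% plain and 74.6% delayed-entry, against a true 73.5%.

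**The case against.** The study is descriptive, tests no hypothesis, and has OS as a secondary endpoint. Cycles before consent and time to consent will be reported, and SAP 8.4 leaves room for other methods. The worst coverage needs both exponential early mortality and consent spread over six cycles, and nothing in the documents says late consent is typical. Since the on-study dose may fall on the day of consent, consent may well cluster at the cycle 2 visit, where delayed entry adds almost nothing.

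Most of this stands as a limit on size and on the remedy. It does not remove the bias: a table of delays does not let a reader correct the curve, and SAP 8.4 names neither a method nor a trigger.

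Four stronger readings are tempting and are not supported:
- *PFS is certainly inflated because early progressors are missing.* Progression before consent is not an exclusion (Protocol 4.3.1), treatment may continue past it (Protocol 5.1.1), and progression is dated from scans ("All tumor assessment dates will be based on the actual imaging dates reported by the investigator") timed by the clinician. This part of the PFS bias is conditional.
- *PFS is unbiased if all early progressors enrol.* It is not, because deaths before consent are still lost.
- *Delayed-entry PFS is the corrected value.* Patients who progressed before entry drop out of it, so it can introduce its own selection.
- *Agreement between the two OS curves shows the bias is small.* The clustered case shows otherwise.

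**Conclusion.** The concern holds in a limited form. Unadjusted OS is left-truncated and biased upward if any eligible patient dies between first dose and consent. PFS shares that part, and any further PFS bias from missing early progressors depends on who enrols.

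The direction follows from the documents; the size does not. Under the assumptions above, 12-month OS rises by 0.7 to 2.0 points for consent within one to three cycles and by 4.0 within six (exponential), or by 0.1 to 1.4 points across all four cases (shape 1.5). This is within sampling error unless consent is late and early mortality is not low. The figures rest on assumed delay distributions and survival shapes, on cited medians from another population, and, in the simulations, on censoring counted from consent rather than from the Index Date.

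**What to change.** Keep the protocol estimates and add the following to the SAP.

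1. In 9.4.2, a delayed-entry Kaplan-Meier sensitivity analysis for OS with origin Day 1, overall and by prior antiangiogenic use, with numbers at risk. Start the curve at a pre-stated minimum risk set (for example 10% of the group, 30 of 300), report that time, and label the curve as conditional on survival to it.
2. State the entry date: the consent date, or the Index Date if a first on-study dose is needed to be in the data. Protocol 6.1 makes this a real choice, because entering patients too early leaves death-free time uncorrected.
3. For PFS, report how many patients progressed before that entry date and state that unadjusted PFS may be biased upward. Any delayed-entry PFS curve is supportive only.
4. Show time from first dose to consent by prior antiangiogenic use.
5. State the limits: delayed entry assumes entry time is independent of prognosis, cannot correct for deaths before the earliest entries, and agrees with the plain curve when consent clusters at cycle 2, even though both are then biased.

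The cost is SAP wording and an entry-time option in the program. SAP 9.2 already needs the first-dose and consent dates. The CI half-width for 12-month OS rises from 4.7–4.9 to 5.1–5.8 points (exponential, start at 30 at risk). There is little or no gain if consent is early or clustered, or if early mortality is low.
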